**7.3.3.8 FDA Expedited Reporting requirements for studies conducted under an IND:**

A sponsor must report any suspected adverse reaction that is both serious and unexpected to the FDA. The sponsor must report an adverse event as a suspected adverse reaction only if there is evidence to suggest a causal relationship between the drug and the adverse event. Refer to Section 7.1.2 for the definition of SAR.

The sponsor must submit each IND safety report on FDA Form 3500A.

Timing

FDA must be notified of potential serious risks within 15 calendar days after the sponsor determines the event requires reporting. FDA must be notified of unexpected fatal or life-threatening suspected adverse reactions as soon as possible but in no case later than 7 calendar days after the sponsor's initial receipt of the information. If the results of a sponsor's investigation show that an adverse event not initially determined to be reportable is reportable, the sponsor must report such suspected adverse reaction in an IND safety report as soon as possible, but in no case later than 15 calendar days after the determination is made.

#### Follow-up

The sponsor must promptly investigate all safety information it receives. Relevant follow-up information to an IND safety report must be submitted as soon as the information is available.

#### Notification of Investigators

The sponsor must notify all participating investigators (i.e., all investigators to whom the sponsor is providing drug under its INDs or under any investigator's IND) in an IND safety report of potential serious risks, from clinical trials or any other source, as soon as possible, but in no case later than 15 calendar days after the sponsor determines that the information qualifies for reporting.

#### Process

If the sponsor deems that an event is both a serious SAR AND unexpected, it must also (in addition to Oncore™) be recorded on the MedWatch Form 3500A as per 21 CFR 312.32. Unexpected adverse events or adverse reaction refers to an event or reaction that is not listed in the investigator's brochure or is not listed at the specificity or severity that has been observed; or if an investigator's brochure is not required or available, is not consistent with the risk information described in the general investigation plan or elsewhere in the current IND application.

The FDA must be notified of any unexpected or life-threatening suspected adverse reactions as soon as possible, but no later than 7 calendar days of learning of the event.

#### Additional Reporting Requirements

The following additional items must be reported via IND safety report:

- *Findings from other studies.* The sponsor must report any findings from epidemiological studies, pooled analysis of multiple studies, or clinical studies, whether or not conducted under an IND, and whether or not conducted by the sponsor, that suggest a significant risk to humans exposed to the drug.
- *Findings from animal or in vitro testing.* The sponsor must report any findings from animal or *in vitro* testing, whether or not conducted by the sponsor, that suggest a significant risk in humans exposed to the drug, such as reports of mutagenicity, teratogenicity, or carcinogenicity, or reports of significant organ toxicity or near the expected human exposure.
- *Increased rate of occurrence of serious suspected adverse reactions.*

#### Additional Guidance

Please refer to 21CFR312.32 and "Guidance for Industry and Investigators: Safety Reporting Requirements for INDs and BA/BE Studies" for additional information and reporting requirements. All IND Safety Reports will be submitted in accordance with these regulations/guidances.

### **7.3.3.9 Institutional Biosafety Committee (IBC)**

In addition to the local IRB, any qualifying serious adverse events (SAEs) must be reported to the Institutional Biosafety Committee (IBC). The IBC is responsible for reviewing recombinant DNA research conducted at or sponsored by the institution for compliance with NIH Guidelines as specified in Section III, Experiments covered by the NIH Guidelines and approving those research projects that are found to conform with the NIH Guidelines. As such, the IBC is charged with ensuring compliance with all surveillance, data reporting and adverse event reporting requirements set forth in the NIH Guidelines.

## **7.4 Data and Safety Monitoring Plan**

The Principal Investigator will provide continuous monitoring of patient safety in this trial with periodic reporting to the Data and Safety Monitoring Committee (DSMC).

Meetings/teleconferences will be held at a frequency dependent on study accrual, and in consultation with the study Biostatistician. These meetings will include the investigators as well as study coordinators, data coordinators, regulatory associates, clinical data management associates, and any other relevant personnel the principal investigators may deem appropriate. At these meetings, the research team will discuss all issues relevant to study progress, including enrollment, safety, regulatory, data collection, etc.

The team will produce summaries or minutes of these meetings. These summaries will be available for inspection when requested by any of the regulatory bodies charged with the safety of human subjects and the integrity of data including, but not limited to, the oversight (Office of Human Research Ethics (OHRE) Biomedical IRB, the Oncology Protocol Review Committee (PRC) or the North Carolina TraCS Institute Data and Safety Monitoring Board (DSMB).

The UNC LCCC Data and Safety Monitoring Committee (DSMC) will review the study on a regular (quarterly to annually) basis, with the frequency of review based on risk and complexity as determined by the UNC Protocol Review Committee. The principal investigator will be responsible for submitting the following information for review: 1) safety and accrual data including the number of patients treated; 2) significant developments reported in the literature that may affect the safety of participants or the ethics of the study; 3) preliminary response data; and 4) summaries of team meetings that have occurred since the last report. Findings of the DSMC review will be disseminated by memo to the principal investigator, PRC, and the UNC IRB.

## 8.0 STATISTICAL CONSIDERATIONS

### 8.1 Study Design/Study Endpoints

A 3 + 3 dose escalation scheme will be used for Dose Level 1 safety run-in followed by Dose Level 2 evaluation for the primary endpoint. In Phase I, patients will be assigned in cohorts of 3, starting with Dose Level 1. The acceptable dose will be defined as the highest dose at which  $\leq 1$  out of 6 patients have experienced a dose limiting toxicity (DLT). We anticipate that 3 patients will be accrued to Dose Level 1 without DLTs and that there will be no DLTs in Dose Level 2 cohort.

The primary study will be the phase II portion (Dose Level 2), where the primary endpoint is rate of resolution of pleural effusion. All patients treated at dose level 2 in Phase I or Phase II, will be included in analyses of safety and efficacy.

### 8.2 Sample Size and Accrual

The null hypothesis that the true rate of resolution of pleural effusion is 45% (Van Meyer 2011) will be tested against a two-sided alternative. The null hypothesis will be rejected if 15 or more responses are observed in 24 patients. A one group chi-squared test with a 0.100 two-sided significance level will have 80% power to detect the difference between the null hypothesis proportion of 45% and the alternative proportion of 70% when the sample size is 24. This sample size was calculated using nQuery Advisor v7.0.

For the phase II portion, sequential boundaries will be used to suspend the trial if excessive numbers of patients experience an unacceptable toxicity. If the study reaches a stopping boundary, it may be terminated by the PI, or submitted to the Data and Safety Monitoring Committee with a description of the failures to date and a rationale for why the study should be continued. An unacceptable toxicity is defined as any grade 3-5 adverse event attributed to therapy (with exceptions; see section 4.1.1 Definitions of Dose Limiting Toxicities (DLT) – Safety Run-in). The accrual will be halted if the number of patients with unacceptable toxicity is equal to or exceeds  $b_n$  out of  $n$  patients with full toxicity follow-up (see table below). This is a Pocock type stopping boundary that assumes that an unacceptable toxicity rate of 0.20 is acceptable. If the true rate is equal to 0.20, the probability of crossing the boundary is 0.05.

Number of Patients, $n$	1	2	3	4	5	6	7	8	9	10	11	12	13	14	15	16	17	18	19	20
Boundary, $b_n$	-	-	3	4	4	4	5	5	6	6	6	7	7	7	8	8	8	8	9	9
Number of Patients, $n$	21	22	23	24	25	26	27	28	29	30										
Boundary, $b_n$	9	10	10	10	11	11	11	11	12	12										

Additionally, during the safety run-in (as indicated in section [4.1.1 of the protocol](#)) if  $\geq 2$  subjects experience a DLT at either dose level then the study will be discontinued.

Any death (other than death related to progressive disease) within 30 days of study drug administration will result in the study pausing whereupon the study will be placed on hold until an appropriate evaluation of the cause of death and a plan of correction, if necessary, is established.

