#### 4.1.3 Definitions of Dose Limiting Toxicities (DLT) – Safety Run-in

A DLT is defined as the development of any new non-hematologic treatment-related grade 3-5 adverse event during or up to 14 days following the third IP dose of talimogene laherparepvec. This results in a 7 week DLT period.

- All subjects with grade 4 DLT events will be permanently discontinued from the study
- All subjects with  $\geq$  grade 3 DLTs of myocarditis or pneumonitis will be permanently discontinued from the study
- I.e., if > 1 scheduled dose of talimogene laherparepvec is missed due to study treatment-related toxicity, talimogene laherparepvec will be permanently discontinued and this event will be considered a DLT

The following adverse events are considered exceptions:

- Grade 3 laboratory-defined events that are asymptomatic and resolve without permanent sequelae to grade 0-1 within a week (ex. a grade 3 LFT

elevation that occurs in the absence of symptoms, resolves to G1 within a week and does not result in any change in liver function).

- Alkaline-phosphatase elevation in patients with known bone metastases
- Pneumothorax, catheter-related complications or other intrapleural effects that are attributed to the standard of care catheter, disease state, or pre-existing medical problems that are not unexpected.
- G3 diarrhea or nausea that resolve to G1 or lower within 48 hours
- Any grade 3-infusion/hypersensitivity reaction symptoms that resolve to grade 0-1 with dose interruption, infusion rate reduction, or supportive care.
- Reactions attributed to nivolumab alone that would be expected in standard of care use may result in permanent cessation of treatment for an individual patient, but will not result in a DLT. Such a patient will be replaced. (Example: an infusion reaction of grade 3 to nivolumab consistent with that occasionally seen in standard of care use).
- Tumor lysis syndrome
- Any AE determined to be unrelated to study treatment
- Events related to disease progression/relapse

In addition, the following will be considered DLTs when treatment-related:

- Pleuritic pain refractory to opioid therapy
- Acute respiratory distress syndrome

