##### **4.4.1 Special warnings and precautions**

- Nivolumab is associated with immune-related AEs. Subjects should be monitored continuously as an AE with nivolumab may occur at any time during or after discontinuation of therapy.

- For suspected immune-related reactions, adequate evaluation should be performed to confirm etiology or exclude other causes. Based on the severity of the adverse reaction, nivolumab should be withheld and corticosteroids administered. If immunosuppression with corticosteroids is used to treat an AE, a taper of at least 1-month duration should be initiated upon improvement. Rapid tapering may lead to worsening of the AE. Non-corticosteroid immunosuppressive therapy should be added if there is worsening or no improvement despite corticosteroid use.

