## 6.5 Post-Treatment/Follow-up Assessments

### 6.5.1 End of Treatment Safety Run-in/Phase II expansion (6.1, 6.2) (+/- 7 days)

Physical examination (including weight and symptom directed medical history)

ECOG Performance Status (see appendix A)

Laboratory evaluations:

- CBC with differential
- Serum chemistries (potassium, sodium, calcium, creatinine, chloride, glucose, magnesium, phosphorus, BUN, albumin, uric acid, and total protein)
- Liver function tests (total bilirubin, direct bilirubin, alkaline phosphatase, AST, ALT)
- Blood/urine/pleura samples to assess viral shedding. Pleural fluid will be separated by the LCCC Immune Monitoring and Genomics Facility (IMGF) into two portions: one portion will be used for correlative studies, and the second portion will be distributed to the CTU laboratory for long term storage at  $-80^{\circ}\text{C}$  for possible assessment of viral shedding for up to two years after study completion. If insufficient amount of pleural fluid is collected, priority will be given to a sample used for correlative studies.
- Blood samples collected for correlative studies

Concomitant medication(s): All concomitant medications will be recorded.

Toxicity evaluation: Use NCI CTCAEv5.0

Collection of Pleural drainage if feasible

Modified Borg Scale of Perceived Dyspnea (Provided in 11.6 Appendix F: Borg Scale): Scale ranging from 0 to 10, which evaluates perceived level of shortness of breath.

Patient diaries

Chest x-ray as needed and/or after three consecutive drainages with  $\leq 50$ cc drainage (every other day drainages) of pleural fluid drainage accompanied by patient-defined improvement in symptoms (cough, chest pain and/or dyspnea).

The end of treatment/safety follow up visit should only occur when patients permanently stop study treatment and should be performed 30 days (+/-7 days) after the last dose of study medication. Patients who have on ongoing  $\geq$ grade 2 or serious AE (SAE) at this visit will continue to be followed until the event is resolved or deemed irreversible by the investigator.

Subjects discontinuing nivolumab should be monitored for at least 100 days after discontinuing the drug for the emergence of SAEs.

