## 7.0 ADVERSE EVENTS

### 7.1 Definitions

#### 7.1.1 Adverse Event (AE)

An adverse event (AE) is any untoward medical occurrence (e.g., an abnormal laboratory finding, symptom, or disease temporally associated with the use of a drug) in a patient or clinical investigation subject administered a pharmaceutical product and which does not necessarily have a causal relationship with this treatment. An AE can therefore be any unfavorable and unintended sign (including an abnormal laboratory finding), symptom, or disease temporally associated with the use of a medicinal product, whether or not related to the medicinal product.

Hospitalization for elective surgery or routine clinical procedures that are not the result of an AE (e.g., surgical insertion of central line) need not be considered AEs and should not be recorded as an AE. Disease progression should not be recorded as an AE, unless it is attributable by the investigator to the study therapy.

From the time of treatment through 30 days following cessation of treatment, all adverse events must be reported by the investigator. Such events will be recorded at each examination on the Adverse Event case report forms/worksheets. The reporting timeframe for adverse events meeting any serious criteria is described in section 7.3. The investigator will make every attempt to follow all subjects with non-serious adverse events for outcome.

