## 7.3 SAEs or Serious SARs

### 7.3.1 Timing

After informed consent but prior to initiation of study medications, only SAEs caused by a protocol-mandated intervention will be collected (e.g., SAEs related to invasive procedures such as biopsies, medication washout).

For any other experience or condition that meets the definition of an SAE or a serious SAR, recording of the event must begin from day 1 of study treatment and continue at least through the 100 day follow-up period after treatment is discontinued. Ultimately, the event should be followed until resolution of symptoms or the investigator determines that symptoms have improved to the fullest extent possible.

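### The automatic death pause in Section 8.2 misses treatment-related deaths more than 30 days after a dose and progression deaths attributed to study therapy

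*Combined protocol and SAP*

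**What the plan says.** **Pause rule.** Section 8.2 states: "Any death (other than death related to progressive disease) within 30 days of study drug administration will result in the study pausing". The hold lasts until the cause has been evaluated and any corrective plan is in place. The section does not say whether study drug means talimogene, nivolumab or either.

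**SAE follow-up.** Under 7.3.1, recording of an SAE must "continue at least through the 100 day follow-up period after treatment is discontinued". Section 6.5.1 adds: "Subjects discontinuing nivolumab should be monitored for at least 100 days after discontinuing the drug for the emergence of SAEs".

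**Progression.** Section 7.1.1 states: "Disease progression should not be recorded as an AE, unless it is attributable by the investigator to the study therapy". Neither the exemption in 8.2 nor the matching entry in the list of DLT exceptions in 4.1.3, "Events related to disease progression/relapse", carries that qualifier.

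**Phase II toxicity boundary.** Section 8.2 says: "An unacceptable toxicity is defined as any grade 3-5 adverse event attributed to therapy", less the DLT exceptions (cited there as 4.1.1, but located in 4.1.3). Patients count once they have full toxicity follow-up, whose length is not given.

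**Late toxicity.** Section 5.2.8 reports that immune-mediated pneumonitis and colitis under nivolumab have included fatal cases. When corticosteroids are used for an adverse event, "a taper of at least 1-month duration should be initiated upon improvement" (4.4.1). Section 4.3.2.4 allows dosing interruptions beyond 6 weeks for prolonged tapers.

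**The concern.** The pause is the only rule in the plan under which one death by itself stops the study for review. Two kinds of death that the plan would recognise as related to treatment fall outside it.

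- A death judged related to study therapy that occurs more than 30 days after the last administration.
- A death from progression that the investigator attributes to study therapy, whenever it occurs.

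This is the first intrapleural use of talimogene (4.1.1). At stake is whether enrolment continues by default while such a death is handled through routine channels.

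**Working it through.** **1. When the 30-day window can be missed.** Inputs: cycle 1 lasts 21 days, later cycles 14 days, visit window 2 days either way (Section 6.2 footnotes).

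- On schedule, the longest interval between doses is 21 + 2 + 2 = 25 days, so a patient stays inside 30 days.
- One skipped 14-day dose: 14 + 14 = 28 days nominally, still inside.
- Two skipped doses: 3 × 14 = 42 days, outside.
- A steroid taper that starts t days after the last dose and lasts at least a month ends no earlier than day t + 30, which is past day 30 for any t above 0. If neither drug has been given again, the patient is still being treated for toxicity when the window closes.

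The gap is therefore confined to patients whose drug is held or stopped. Whether nivolumab given alone after the effusion resolves restarts the clock depends on the undefined term study drug.

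**2. The plan's own boundary figure.** Let P(n,k) be the probability of k toxicities in n patients without an earlier crossing. The recursion is P(n,k) = (1−p)·P(n−1,k) + p·P(n−1,k−1), absorbing whenever k reaches the printed boundary. At p = 0.20 the crossing probability is 0.0495 over the full table (n to 30), which reproduces the stated 0.05. It is 0.0451 if the table stops at the planned 24.

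**3. What one late related death does to that boundary.** It adds at most one count.

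| Patients n | Boundary | Further counts needed |
|---|---|---|
| 3 | 3 | 2 |
| 4 to 6 | 4 | 3 |
| 10 | 6 | 5 |
| 24 | 10 | 9 |

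It adds none if it falls after the undefined toxicity follow-up, or if it is classed under the 4.1.3 exception for expected reactions to nivolumab alone.

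The documents give no rate for such deaths. As an illustration, assume a rate q per patient, no other counted toxicity, and 24 patients. Then P(at least one) = 1 − (1−q)^24, and the crossing probability comes from the same recursion with p = q.

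| Assumed q | P(at least one) | P(boundary crossed) |
|---|---|---|
| 0.02 | 0.38 | 0.00001 |
| 0.05 | 0.71 | 0.0002 |
| 0.10 | 0.92 | 0.0024 |

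A boundary built around a 20% toxicity rate is not designed to react to single deaths, and does not.

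**4. A progression death attributed to therapy.** Under 7.1.1 it is an adverse event. Read with the boundary definition in 8.2, a grade 5 event attributed to therapy would add one count. If the imported progression exception in 4.1.3 is read to apply, it adds none. The text does not settle which. On either reading the pause does not trigger.

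**5. The other safeguards.**

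| Safeguard | Section | Why it is not an automatic pause for one such death |
|---|---|---|
| SAE entry within 24 hours | 7.3.2 | Recording only |
| IRB notice within 7 days | 7.3.3.1 | Only if an Unanticipated Problem |
| Report to Amgen | 7.3.3.6 | Report only |
| FDA report within 7 days | 7.3.3.8 | Only if unexpected; a reaction already listed could be classed as expected |
| Biosafety committee report | 7.3.3.9 | Qualifying SAEs; report only |
| DSMC review | 7.4 | Quarterly to annually |
| Run-in rule | 4.1.1, 8.2 | Needs two DLTs, within a 7-week period |

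**The case against.** The strongest reply is that an SAE collection period and a halting trigger serve different purposes and need not have the same length. Thirty days also has support in the plan: "From the time of treatment through 30 days following cessation of treatment, all adverse events must be reported by the investigator" (7.1.1), and the end-of-treatment visit falls at 30 days. That stands. The two windows differ, but they do not contradict each other.

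A second reply is that exempting progression is sensible in this population. Section 1.2 gives a median survival of four months. Under an assumed exponential survival time, about 16% would die of any cause by day 30 and about 43% by day 100, so a trigger on every death over 100 days would be unworkable. This is a good argument against an all-cause 100-day trigger. It has less force against a trigger limited to deaths judged related, because the FDA and Amgen reports already require that judgement.

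Third, the run-in is better protected than the boundary table suggests. Two DLTs at a dose level discontinue the study, and each patient completes 7 weeks before the next is enrolled. That also stands, so the gap matters mainly in the phase II expansion and for deaths after the 7-week period.

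Several stronger readings are tempting and are not supported:

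- A reader might infer that treatment-related deaths in general escape the pause. Any non-progression death within 30 days of a dose pauses the study, whatever its cause.
- A reader might infer that a late fatal event goes unreviewed. The reporting duties listed above contradict that.
- A reader might subtract 30 from 100 and quote 70 uncovered days, or a share of deaths missed. The 30 days run from a dose and the 100 from discontinuation of treatment, so the subtraction works only once dosing has stopped. The documents give no distribution of time to death from which a share could be computed.
- A reader might take the account of effusion formation in 1.2 to mean that therapy-provoked worsening is expected. That section describes disease mechanisms, with the inflammatory-mediator evidence from mouse models, and says nothing about study therapy provoking effusion.

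**Conclusion.** The point holds in limited form. A related death more than 30 days after the last dose, and a progression death attributed to therapy, trigger no automatic pause. The first adds at most one count to a boundary of 3 to 10 over the planned 24 patients; the second adds one or none, depending on how 4.1.3 is read. No other provision pauses the study for a single such death.

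This rests on the wording of 8.2 as printed and, for the window gap, on dosing having been held or stopped for more than 30 days. The number of deaths affected cannot be estimated from the documents, and the crossing probabilities above depend on assumed rates. It is an inexpensive safety improvement, not an error that invalidates the design.

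**What to change.** In Section 8.2:

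1. Keep the present 30-day trigger.
2. Add to the pause rule any death judged at least possibly related to study therapy within the SAE follow-up period already set by 7.3.1.
3. Qualify the progression exemption as 7.1.1 does, so that it does not cover progression that the investigator attributes to study therapy.
4. State which agents count as study drug for the 30-day clock, state the length of full toxicity follow-up, and correct the cross-reference for the DLT exceptions to 4.1.3.

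Separately, the progression exception in 4.1.3 and the attribution clause in 7.1.1 must be reconciled, so that it is clear whether a therapy-attributed progression death counts toward the boundary. How the DLT definition should read is for the investigators to decide.

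The cost is amendment wording and an occasional short hold to review a late death judged related. Sample size, visits and data collection do not change.
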